## 4.7. Other Analysis

## 4.7.1. Subgroup analyses

N/A.

## 4.8. Interim Analyses

No interim analysis requiring statistical adjustment will be performed. Immunogenicity analysis will be performed on PPS, while safety analyses will be performed on Solicited Set for solicited AEs, Exposed Set for lab and unsolicited AEs. However, analyses to evaluate objectives and endpoints will be performed in steps. The sequence of analyses is described below.

## 4.8.1. Sequence of analyses

- In preparation of the safety review during the dose-escalation safety lead-in, analyses of available safety data will be performed.
- **Day 15 interim analysis** for each group in Part A of the study will include all the data (Day 1 and Day 15) pertaining to primary and secondary safety endpoints; humoral immunogenicity endpoints (including at least neutralizing titer against pseudovirus bearing S protein from vaccine encoded SARS-COV-2 endpoints). This analysis will be performed when all data of each study group up to Day 15 (i.e., data that are as clean as possible) are available.
  - Results of this analysis will be presented in a Day 15 statistical analysis report.
  - This analysis will be performed by independent unblinded statistician who will be unblinded for this analysis, who will generate a statistical report by treatment group but no individual listings.
  - GSK restricted unblinded team will have access to the unblinded individual data.
  - The investigators and study participants will stay blinded (i.e., will not have access to the individual participant treatment assignment) until EoS.
  - For subsequent analyses the GSK statistical team will be unblinded to individual participants.
  - A similar to Part A Day 15 interim analysis for each group in Part B of the study may be conducted separately or incorporated into a Day 31 interim analysis.
- **Day 31 interim analysis** for each group in Part A of the study will include all the data (Day 1, Day 15, and Day 31) pertaining to primary and secondary safety endpoints; humoral immunogenicity endpoints (including at least neutralizing titer against pseudovirus bearing S protein from vaccine encoded SARS-COV-2 endpoints). This analysis will be performed when all data of each study group up to Day 31 (i.e., data that are as clean as possible) are available.
  - Results of this analysis will be presented in a Day 31 statistical analysis report.

#### CONFIDENTIAL

- The investigators and study participants will stay blinded (i.e., will not have access to the individual participant treatment assignment) until EoS.
- A similar to Part A Day 31 interim analysis for each group in Part B of the study may be conducted separately or incorporated into the final analysis.
- The final analysis will include all data from Part A and B pertaining to primary and secondary safety and immunogenicity endpoints, and any available tertiary endpoint(s). This analysis will be performed at the EoS when all data up to study conclusion (Month 6) are available, this includes Day 1, Day 15, Day 31, and Month 6, as all the data analyzed in the Day 15 and Day 31 analyses will be included in the final analysis as well.

The final study report will contain at least the final analyses of all primary and secondary endpoints, including individual listings.

If the data for tertiary endpoints become available at a later stage, (an) additional analysis/ analyses will be performed. These analyses will be documented in annex(es) to the study report.

## 4.9. Changes to Protocol Defined Analyses

Because RT-PCR at screening and Day 1 do not contribute to the incidence of SARS-CoV-2 infection they have been removed from the SARS-CoV-2 infection endpoint and summary.

# 5. SAMPLE SIZE DETERMINATION

The sample size is based on clinical considerations to inform dose regimen decisions for continued clinical development.

With 18 participants receiving mRNA-CR-04 vaccine in each group, there is a 60.3% probability to observe at least one participant with an AE if the incidence rate is 5% and 85% probability to observe at least one participant with an AE if the incidence rate is 10%.

With 16 participants receiving mRNA-CR-04 vaccine in each group (PPS for immunogenicity, 10% unevaluable), and a standard deviation of 0.45 for log10 transformed increase from Day 1, the ratio of the upper limit of a 2-sided 95% CI and the point estimate of GMR is 1.74.

## 6. SUPPORTING DOCUMENTATION

## 6.1. Appendix 1 Study Population Analyses

## 6.1.1. Participant Disposition

Participant disposition will be summarized by treatment and overall using descriptive statistics:

• Number of participants screened, randomised, vaccinated including withdrawal reasons will be tabulated.

Withdrawal status will be summarized using descriptive statistics:

- The number of participants exposed as well as the number of participants excluded from PPS analyses will be tabulated at D15, D31, and M6.
- The numbers of withdrawn participants will be tabulated according to the reason for withdrawal.

## 6.1.2. Demographic and Baseline Characteristics

#### 6.1.2.1. Analysis of demographics/baseline characteristics

These analyses will be performed on the Exposed set and PP set at Day 15, Day 31.

The demographic characteristics including height, weight, body mass index (BMI), age at screening in years, sex, race, ethnicity, and N protein) will be summarized by treatment using descriptive statistics.

- Frequency tables will be generated for categorical variable such as sex, race and ethnicity.
- Mean, median, standard error and range will be provided for continuous data such as age, height, weight and BMI.

The distribution of participants will be tabulated as a whole and per treatment group.

## 6.1.2.2. Additional considerations

- Demographic characteristics will also be summarized on Enrolled Set for web public disclosure for Part A and Part B separately.
- The listing of past medical history and current medical conditions will be provided on the Exposed Set by Medical Dictionary for Regulatory Activities (MedDRA) term for Part A and Part B separately. Un-coded medical conditions or medical history will be listed under 'Other' category.
- Vaccination history will be coded using WHODRUG dictionary. The listing of vaccination history will be provided on the Exposed Set for Part A and Part B separately.

## 6.1.3. Protocol Deviations

Important protocol deviations will be listed based on the Exposed Set for Part A and Part B separately.

Protocol deviations will be tracked by the study team throughout the conduct of the study. These protocol deviations will be reviewed to identify those considered as important as follows:

- Data will be reviewed prior to freezing the database to ensure all important deviations captured and categorised in the protocol deviations dataset.
- This dataset will be the basis for the summaries of important protocol deviations.
- A listing of protocol deviations will be provided.

Protocol deviations which result in exclusion from the analysis set will also be listed.

• Data will be reviewed prior to freezing the database to ensure all deviations leading to analysis population exclusions are captured and categorised in the protocol deviations ADaM dataset (note these exclusions are not captured in the SDTM dataset).

In addition to the overall listing of important protocol deviations, separate listings will be produced for important protocol deviations related to COVID-19, and important protocol deviations not related to COVID-19 respectively if deemed necessary.

An individual listing of important protocol deviations leading to elimination will be provided.

## 6.1.4. Concomitant Medications

Concomitant medications and vaccinations will be coded using the WHODRUG dictionary.

The listing of participants taking concomitant medications /vaccinations within 7 days following study intervention administration, and 30 days following study intervention administration will be provided for Part A and Part B separately.

The antipyretic classification is derived from the following ATC code:

ATC Code	
A03D, A03DA, A03DB, A03DC, A03EA	
M01, M01A, M01AA, M01AC, M01AE, M01AG, M01AB, M01AH, M01AX, M03B, M03BA, M03BB, M03BC, M03BX	
N02BG, N02AC, N02AG, N02AX, N02B, N02BA, N02BB, N02BE, N02AA	
R05, R05D, R05X	

The number and percentage with exact 95% CI of participants reporting concomitant medication coded using the WHODRUG dictionary (any medication or any antipyretic) during the 7-day follow-up period (i.e. from Day 1 - Day 7) and during the 30-day

follow-up (i.e. from Day 1- Day 30) will be summarized by treatment group for Part A and Part B separately.

The analysis will be performed on the Exposed Set.

## 6.1.5. Additional Analyses Due to the COVID-19 Pandemic

Depending on how the Covid-19 situation evolves, the SAP might be amended to reflect the analysis corresponding to Covid-19.

## 6.2. Appendix 2 Data Derivations Rule

## 6.2.1. Study Day and Reference Dates

The safety reference date is the study intervention start date and will be used to calculate study day for safety measures.

The study day is calculated as below:

- Assessment Date = Missing  $\rightarrow$  Study Day = Missing
- Assessment Date < Reference Date  $\rightarrow$  Study Day = Assessment Date Ref Date
- Assessment Data  $\geq$  Reference Date  $\rightarrow$  Study Day = Assessment Date Ref Date + 1

## 6.2.2. Handling of missing data

#### 6.2.2.1. Dates

Partial dates will be displayed as captured in participant listing displays.

When partially completed dates (i.e. with missing day or month) are used in calculations, the following standard rules will be applied:

- A missing day will be replaced by 15;
- A missing day and month will be replaced by June 30th;
- For stop date, the maximum between the start and imputed stop date by above rule will be used instead.

The following exceptions apply:

- Adverse events start dates on the same day as the vaccination but with missing time:
  - Onset day will be day 1.
- Adverse event start dates with missing day:
  - If the event starts in the same month as the study intervention administration, then the imputed start date will match the study dose given during that month.
- Adverse event start dates with missing day and month:
  - If the event starts in the same year as the study intervention administration, the imputed start date will match the study dose given during that year.

- Adverse event end dates with missing day:
  - If the event ends in the same month and year as the end of study date (if it exists) then the imputed end date will match the end of study date;
  - Otherwise, day will be imputed to the last day of the month.
- Adverse event end dates with missing day and missing month:
  - If the event ends in the same year as the end of study date (if it exists) then the imputed end date will match the end of study date
  - Otherwise, day and month will be imputed to the last day and month of the year i.e. 31st DEC

All other cases of incomplete AE or concomitant medication/vaccination start date will follow the standard rules above.

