# 8.4.1. Time period and frequency for collecting AE, SAE and other safety information

All SAEs will be collected from the start of study intervention until Visit 5 at the time points specified in the SoA (Section 1.3).

SAEs assessed as related to study participation (e.g., study intervention, protocolmandated procedures, invasive tests, or change in existing therapy) or related to a GSK product (non-IMP) will be recorded from the time a participant consents to participate in the study.

All AEs will be collected from the start of study intervention until Visit 4 at the timepoints specified in the SoA (Section 1.3).

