## 4.2. Primary Endpoint(s) Analyses

## 4.2.1. Safety and Reactogenicity

## 4.2.1.1. Analysis of safety and reactogenicity planned in the protocol

Solicited safety endpoints will be performed on the Solicited Safety Set. Unsolicited safety endpoints will be performed on the Exposed Set. Other adverse events/medically attended events, and safety lab data will be performed on the Exposed Set.

Primary Safety Endpoints	Statistical Analysis Methods
Solicited administration site events and systemic events during the 7-day follow-up period after study vaccine administration (day of study vaccine administration and 6 subsequent days);	Solicited AEs are prespecified as administration site and systemic. Solicited AEs are AEs with onset from Day 1 – Day 7 after the dosing and captured in eDiary. The number and percentage with exact 95% Cl of participants reporting at least one solicited administration site event, with at least one solicited systemic event, and with any solicited AE during the 7- day period (i.e. with onset from Day 1- Day 7 post vaccination) will be tabulated by treatment group. The same tabulations will be performed for Grade 3 AEs.
	The number and percentage with exact 95% CI of participants reporting each individual solicited administration site event (any grade, Grade 1, Grade 2, Grade 3, medically attended events) and solicited systemic event (any grade, Grade 1, Grade 2, Grade 3, medically attended events) during the 7-day follow-up period (i.e. with onset from Day 1- Day 7 post vaccination) will be tabulated by maximum intensity per participant for each treatment group.
Unsolicited AEs during the 30-day follow-up period after study vaccine administration (day of study vaccine administration and 29 subsequent days);	The number and percentage with exact 95% CI of participants reporting at least one unsolicited AE during the 30-day follow-up period (i.e. with onset from Day 1 to Day 30 post vaccination), as classified by the Medical Dictionary for Regulatory Activities (MedDRA) System Organ Class (SOC) and Preferred Term (PT) will be tabulated by treatment group.
	The same tabulations will be performed for Grade 3, any causally related, Grade 3 causally related unsolicited AEs and unsolicited AEs with medically attended visits. In the AE summaries, a participant with 2 or more AEs within the same SOC or PT level but different relationship will be counted only once in the level using the related incident.

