Any hematological and biochemical laboratory abnormality during the 15-day follow-up period after study vaccine administration (day of study vaccine administration and 14 subsequent days);	
 
For each treatment group and for each Hematology and biochemistry parameter:
 
The number and percentage with exact 95% CI of participants having hematology and biochemistry results below, within, or above the laboratory normal ranges will be tabulated by time point.
 
The number and percentage of subjects reporting a grading increase from baseline at Day 8 and
 

Primary Safety Endpoints	Statistical Analysis Methods
	Day 15 separately. The maximum grading post
	vaccination up to Day 15 (i.e. Day 1 – Day 15) will
	be tabulated versus baseline. Grades will be
	based on the FDA guidance for industry "Toxicity
	grading scale for healthy adults and adolescent
	volunteers enrolled in preventive vaccine clinical
	trials" (Protocol Section 10.2.2).
	The listing of safety laboratory results will be
	provided
MAAEs; SAEs; AESIs up to D31.	The number and percentage with exact 95% CI of
	participants reporting MAAEs, SAEs, and AESIs after
	the dose up to Day 31 (i.e. with onset from Day 1 to Day
	30 post vaccination), as classified by the MedDRA SOC
	and PT, will be tabulated by treatment group. The same
	tabulation will be performed for causally related MAAEs,
	SAEs and AESIs during this period (i.e. with onset from
	Day 1 to Day 30 post vaccination).
	The detailed listings of SAEs, AESIs and COVID-19
	cases will also be produced.

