#### 6.2.3.7. Onset day

The definition of onset day for an event (e.g. AE, concomitant medication/vaccination) is the number of days between the last study dose and the start date of the event. This is 1 for an event occurring on the same day as a study dose (and reported as starting after study dose).

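### An unsolicited AE starting in the month after dosing with its day unknown is dated the 15th, which for doses in roughly the first half of a month falls outside the primary Day 1-30 window and can postdate the AE's own report

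*SAP*

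**What the plan says.** SAP 6.2.2.1 sets the standard rule: "A missing day will be replaced by 15". For an AE start date with only the day missing there is one exception: "If the event starts in the same month as the study intervention administration, then the imputed start date will match the study dose". The section then closes the list: "All other cases of incomplete AE or concomitant medication/vaccination start date will follow the standard rules above". Its only consistency guard applies to imputed stop dates, which may not precede the start. No guard ties an imputed start to the report date, to Visit 4 or to a known end date.

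The primary unsolicited AE table in SAP 4.2.1.1 selects on onset: "i.e. with onset from Day 1 to Day 30 post vaccination". The primary row for "MAAEs; SAEs; AESIs up to D31" uses the same window. SAP 6.2.3.7 fixes the day count: "This is 1 for an event occurring on the same day as a study dose".

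On collection, Protocol 8.4.1 states: "All AEs will be collected from the start of study intervention until Visit 4". Protocol Table 2 allows Visit 4 at 27-33 days after Visit 1, which is study Day 28-34. MAAEs, SAEs and AESIs are collected to Month 6.

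**The concern.** A 30-day window usually runs into the following month, and an AE reported at Visit 4 can easily be recorded with the month known and the day forgotten. If the dose was given early in the month, the 15th of the next month lies beyond the window and may lie beyond the visit at which the participant described the event. The rule then produces an impossible onset date and removes from the primary safety table an event that was known to have started by Visit 4.

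The rule also runs against its neighbours. A missing day in the dosing month becomes the dose date. A missing day and month in the dosing year also becomes the dose date. So an AE for which only the year is known stays in the primary table, while the same AE with its month known can drop out. That looks like an oversight rather than a choice.

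With 18 vaccinees per dose group, one participant missing from a row is 1/18 = 5.6 percentage points.

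**Working it through.** **Inputs.** Dose day is Day 1 (SAP 6.2.3.7). Window is Day 1-30 (SAP 4.2.1.1). Imputed day is the 15th (SAP 6.2.2.1). Visit 4 is nominally Day 31, allowed Day 28-34 (Protocol Table 2).

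**Formula.** For a dose on day d of a month with L days and an AE in the next month with day unknown:

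imputed onset day = (L - d) + 15 + 1 = L - d + 16.

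This exceeds 30 when d ≤ L - 15, and exceeds 34 when d ≤ L - 19.

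| Length of dosing month | Dose days imputed past Day 30 | Dose days imputed past Day 34 |
|---|---|---|
| 31 | 1-16 | 1-12 |
| 30 | 1-15 | 1-11 |
| 29 | 1-14 | 1-10 |
| 28 | 1-13 | 1-9 |

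**One record.** Dose on 5 March, Visit 4 on 4 April (Day 31), AE reported at that visit as starting in April, day unknown. True onset is 1-4 April, Day 28-31. The rule gives 15 April: 31 - 5 + 16 = Day 42, eleven days after the report and outside the table. If the site had also recorded an end date of 4 April, the duration formula in SAP 6.2.3.8 would give 4 - 15 + 1 = -10 days.

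**Size.** Take every dose date in a 366-day year and true onset uniform over Day 1-30, which gives 366 × 30 = 10,980 combinations.

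- In-window days in the next month for dose day d: d + 29 - L, where positive. Summed over a month this is 1 + 2 + ... + 29 = 435; over twelve months, 5,220.
- Of these, the combinations with d ≤ L - 15 are moved past Day 30: 1 + 2 + ... + 14 = 105 per month, 1,260 in all.
- Moved out of the window: 1,260/10,980 = 11.5% of AEs with missing day, or 1,260/5,220 = 24.1% of those starting in the following month.
- Dated past Day 34: 1 + 2 + ... + 10 = 55 per month, 660 in all; 660/10,980 = 6.0%.

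A 365-day year gives the same figures to the first decimal.

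**Translated to all unsolicited AEs.** The documents do not give the share with a missing day. At an assumed 1%, 0.01 × 11.5% = 0.1%; at 5%, 0.05 × 11.5% = 0.6%.

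**Candidate repairs on the same grid.**

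- First of the month: onset day is L - d + 2, which is at most 30 whenever any next-month date is in the window. None of the 1,260 combinations stays out.
- Earlier of the 15th and the report date, with first report at the nominal Visit 4: the imputed day is Day 31 for all 1,260, so all remain excluded. In the 5 March record it gives 4 April, Day 31. The cap removes impossible dates but does not restore these events.

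**The case against.** A reader might infer that the rule suppresses primary safety events in general, including MAAEs, SAEs and AESIs. The documents do not support that. These events are collected to Month 6, so one in the following month may truly start after Day 30, and one that leaves the Day 31 table stays in the Month 6 table. With onset uniform over Day 1-60 (an assumption) and following-month events only, the 15th wrongly moves 11.3% out and 13.7% in, which is roughly balanced. First-of-month imputation would wrongly move 48.4% in, or 68.8% for doses on days 1-15. The claim of under-counting, and the first-of-month remedy, therefore belong to unsolicited AEs only.

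Even there, the 11.5% counts losses alone. For a true onset on Day 31, the present rule already moves about 51% of missing-day records into the window.

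A reader might also infer that events vanish from the report. They do not: partial dates appear in listings as captured, and all solicited and unsolicited AEs are listed (SAP 4.2.1.2.3).

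Finally, the effect is very small. The trial has about 114 participants and only descriptive analyses. At an assumed 100 unsolicited AEs, the expected loss is 0.1-0.6 of one event. SAEs and AESIs are reportable within 24 hours, so an unknown onset day is less likely for them.

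All of this stands. It limits scope and size. It does not remove the fact that a stated rule can date an unsolicited AE after its own report and exclude it from the table it belongs in.

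**Conclusion.** The point holds for unsolicited AEs. As written, SAP 6.2.2.1 yields onset dates that cannot be true, and for dose days up to 13-16, depending on month length, it takes following-month events out of the primary Day 1-30 table. For the first day or two of a 30- or 31-day month no next-month date is in the window, so nothing in-window is lost there.

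The size is 11.5% of unsolicited AEs with a missing day, given dose dates spread evenly over the year and true onset uniform over Day 1-30. At an assumed 1-5% with a missing day, that is 0.1-0.6% of unsolicited AEs, and the actual count may be zero. No conclusion of the trial is likely to turn on it. It is a low-priority correction, worth making because it is cheap and because the neighbouring rules already lean the other way.

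**What to change.** Add one exception to SAP 6.2.2.1 for an AE start date with missing day in a month after the dosing month:

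- Unsolicited AEs that are not serious, not AESIs and not medically attended: impute the first day of that month, in line with the treatment of the dosing month.
- MAAEs, SAEs and AESIs: keep the 15th, but cap it at the date the event was first reported and at any known end date, so that no onset is later than its own report.

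The cost is a short addition to the SAP and the matching derivation code, which must read the seriousness, AESI and medically attended flags.

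Two limits should be stated with it. First, most missing-day onsets on Day 31-34 will now count as in the window. An onset on Day k escapes only if it falls on the 1st to the (k - 30)th of a month, so (366 - 12)/366 = 96.7% are counted in at Day 31 and (366 - 48)/366 = 86.9% at Day 34. Second, the cap alone does not return an MAAE, SAE or AESI first reported on Day 31 or later to the window; such an event remains in the Month 6 table.
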